3.2 Inclusion Criteria

Subject is eligible for the study if all of the following apply.

1. Kidney transplant patient ≥ 16 years and ≤ 70 years old.
2. Institutional Review Board (IRB)-/Independent Ethics Committee (IEC)-approved written Informed Consent and privacy language as per national regulations (e.g., HIPAA Authorization for US sites) must be obtained from the subject or legally authorized representative prior to any study-related procedures (including withdrawal of prohibited medication, if applicable). For subjects < 18 years old, informed consent must be obtained from the subject's parent(s) or legal guardian(s); subject Assent (where appropriate) must be given.
3. Recipient of a de novo kidney from a living or deceased donor. Note: Recipient of an *en bloc* deceased donor kidney transplant from a pediatric donor ≥ 5 years of age AND weighing greater than 20 kg is allowed.
4. If deceased donor, a Kidney Donor Profile Index (KDPI) ≤ 85 [donation after circulatory death (DCD) and what was previously known as extended criteria donor (ECD) organ recipients *are* eligible for enrollment provided KDPI ≤ 85]
5. Removed
6. At least one antigen mismatch at major MHC (class I or class II).
7. Willingness to comply with study protocol.
8. Subject agrees not to participate in another investigational drug study while on treatment.

9. Female subject must be either:
 - a. Of non-child-bearing potential
 - i. Post-menopausal (defined as at least 1 year without any menses) prior to screening, or
 - ii. Documented surgically sterile or status post-hysterectomy
 - b. Or, if of childbearing potential,
 - i. Agree not to try to become pregnant during the study and for 90 days after the final study drug administration
 - ii. And have a negative serum or urine pregnancy test within 7 days prior to transplant procedure
 - iii. And, if heterosexually active, agree to consistently use two forms of highly effective birth control (at least one of which must be a barrier method) which includes consistent and correct usage of established oral contraception, established intrauterine device or intrauterine system, or barrier methods of contraception: condom or occlusive cap (diaphragm or cervical/vault caps) with spermicidal foam/gel/film/cream/suppository or vasectomy in the male partner, starting at screening and throughout the study period and for 90 days after the final study drug administration.
10. Male subject and their female spouse/partners who are of childbearing potential must be using highly effective contraception consisting of two forms of birth control (one of which must be a barrier method) starting at screening and continuing throughout the study period and for 90 days after the final study drug administration (acceptable forms of birth control are listed in Inclusion Criterion 9).
11. Male subject must not donate sperm starting at screening throughout the study period and for 90 days after the final study drug administration.
12. Female subject must agree not to breastfeed starting at screening and throughout the study period, and for 90 days after the final study drug administration.
13. Female subject must not donate ova starting at screening and throughout the study period, and for 90 days after the final study drug administration.
14. Will be receiving induction immunotherapy (either T-cell depleting agent, anti-CD52 monoclonal antibody, or IL-2 co-stimulation blocker), with dose and frequency of the chosen induction agent determined by local standard of care. Steroid-only induction does not satisfy this criterion.

Waivers to the inclusion criteria will **NOT** be allowed.

Previous kidney transplants will be permitted.

Patients who are receiving a secondary transplant and who previously received Astagraf XL or who are currently on Astagraf XL as a component of maintenance immunosuppression and re-listed for transplant will be eligible to enroll in ASTOUND and will be randomized at the time of transplant to either cohort.

3.3 Exclusion Criteria

Subject will be excluded from participation if any of the following apply.

1. Patient is known to have a positive test for latent tuberculosis (TB) and has not previously received adequate anti-microbial therapy or would require TB prophylaxis after transplant.
2. Uncontrolled concomitant infection or any unstable medical condition that could interfere with study objectives.
3. Significant liver disease, defined as having, during the past 28 days, consistently elevated AST (SGOT) and/or ALT (SPGT) levels greater than 3 times the upper value of the normal range of the investigational site.
4. Patient currently taking or maintained on another form of extended-release tacrolimus following his/her transplant procedure.
5. Patient who will be maintained on a non-tacrolimus-based maintenance immunosuppressive regimen following his/her transplant procedure.
6. Patient currently taking, having taken within 30 days, or who will be maintained on an mTOR inhibitor following his/her transplant procedure.
7. Use of an investigational study drug in the 30 days prior to the transplant procedure.
8. Contraindication or hypersensitivity to drugs or any of their components that constitute the immunosuppression regimen.
9. 6 Ag match or zero mismatch at major MHC (class I or class II).
10. Receipt of an ABO-incompatible organ. *Note: A2 donor to O recipient or A2 donor to B recipient is considered ABO-compatible and not excluded by this criterion.*
11. Removed
12. Removed
13. The presence of current *or historic*, pre-formed anti-HLA DSA against the current donor (evidence of pre-formed, *non-donor* HLA is not exclusionary) as defined by a subject meeting any of the following criteria*:
 - a. Positive virtual crossmatch,
 - b. Positive T- or B-cell crossmatch by NIH antiglobulin lymphocytotoxicity method,**
 - c. Positive T- or B-cell flow cytometry crossmatch defined by the MFC criteria used by the center's HLA lab for their local proficiency testing,**
 - d. An MFI greater than or approaching 1000 using flow cytometry/Luminex-based, specific anti-HLA antibody testing.

*Patients are eligible to enroll with a negative virtual crossmatch if used *in lieu* of a physical crossmatch, if, in the opinion of the patient's attending physician, use of such is required to obviate the accrual of excessive ischemia time. However, continued

participation is predicated on the performance of the physical crossmatch within 48 hours of transplant. If the physical crossmatch is positive, the subject will be discontinued.

** If *b* or *c* above are positive secondary to a suspected positive auto-crossmatch, that is not exclusionary as long as *a* and *b* above are not met.

14. Receipt of desensitization, antibody-removal, anti-B-cell, or anti-plasma cell therapy in the 90 days preceding the transplant procedure.
15. Planned initiation (prior to transplant) of desensitization, antibody-removal, anti-B-cell, or anti-plasma cell therapy within 7 days of the transplant procedure.
16. Donor or recipient with known hepatitis C infection (HCV antibody positive), HIV infection (HIV antibody positive), acute hepatitis B infection (HBsAg positive, anti-HBc positive, IgM anti-HBc positive, anti-HBs negative) chronic hepatitis B infection (HBsAg positive, anti-HBc positive, IgM anti-HBc negative, anti-HBs negative), or equivocal hepatitis B status (HBsAg negative, anti-HBc positive, anti-HBs negative). Patients (donor or recipient) who have normal liver function tests (LFT) and who are either hepatitis C positive with a negative viral load or have natural or vaccine-acquired immunity from hepatitis B are not excluded by this criterion.
17. Primary focal segmental glomerulosclerosis.
18. Subject has a current malignancy or history of malignancy (within the past 5 years), except non-metastatic basal or squamous cell carcinoma of the skin or carcinoma-in-situ of the cervix that has been successfully treated.
19. Recipient of multi-organ or dual kidney transplants (inclusive of current transplant and any prior non-renal transplants). *Note: Patients with prior kidney transplants are eligible.*
20. Recipient of an *en bloc*, pediatric deceased donor kidney from a donor less than 5 years of age OR weighing less than 20 kg.
21. Prior graft loss secondary to CMV or BK nephropathy.
22. Prior history of invasive organ disease in the presence of CMV or BKV or clinically significant CMV viremia.
23. History of clinically significant (per investigator's discretion) BK viruria.
24. Any condition which, in the investigator's opinion, makes the subject unsuitable for study participation.
25. Planned complete steroid avoidance. (Steroid initiation and subsequent taper / withdrawal will allowed and will be under the purview of the treating physician.)
26. Planned receipt of post-transplant, prophylactic HCV treatment.

Waivers to the exclusion criteria will **NOT** be allowed.

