6. Patient currently taking, having taken within 30 days, or who will be maintained on an mTOR inhibitor following his/her transplant procedure.
7. Use of an investigational study drug in the 30 days prior to the transplant procedure.
8. Contraindication or hypersensitivity to drugs or any of their components that constitute the immunosuppression regimen.
9. 6 Ag match or zero mismatch at major MHC (class I or class II).
10. Receipt of an ABO-incompatible organ. *Note: A2 donor to O recipient or A2 donor to B recipient is considered ABO-compatible and not excluded by this criterion.*
11. Removed
12. Removed
13. The presence of current *or historic*, pre-formed anti-HLA DSA against the current donor (evidence of pre-formed, *non-donor* HLA is not exclusionary) as defined by a subject meeting any of the following criteria*:
 - a. Positive virtual crossmatch,
 - b. Positive T- or B-cell crossmatch by NIH antiglobulin lymphocytotoxicity method,**
 - c. Positive T- or B-cell flow cytometry crossmatch defined by the MFC criteria used by the center's HLA lab for their local proficiency testing,**
 - d. An MFI greater than or approaching 1000 using flow cytometry/Luminex-based, specific anti-HLA antibody testing.

* Patients *are* eligible to enroll with a negative virtual crossmatch if used in lieu of a physical crossmatch, if, in the opinion of the patient's attending physician, use of such is required to obviate the accrual of excessive ischemia time. However, continued participation is predicated on the performance of the physical crossmatch within 48 hours of transplant. If the physical crossmatch is positive, the subject will be discontinued.

** If *b* or *c* above are positive secondary to a suspected positive auto-crossmatch, that is not exclusionary as long as *a* and *d* above are not met.
14. Receipt of desensitization, antibody-removal, anti-B-cell, or anti-plasma cell therapy in the 90 days preceding the transplant procedure.

15. Planned initiation (prior to transplant) of desensitization, antibody-removal, anti-B-cell, or anti-plasma cell therapy within 7 days of the transplant procedure.

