8.1.6 Protocol Deviations

A protocol deviation is generally an unplanned excursion from the protocol that is not implemented or intended as a systematic change. The investigator is responsible for ensuring the study is conducted in accordance with the procedures and evaluations described in this protocol and for protecting the rights, safety, and welfare of subjects. The investigator should not implement any deviation from, or changes to, the protocol, unless it is necessary to eliminate an immediate hazard to trial subjects.

A protocol waiver is a documented prospective approval of a request from an investigator to deviate from the protocol. Protocol waivers are strictly prohibited.

For the purposes of this protocol, deviations requiring notification to Sponsor are defined as any subject who:

- Entered into the study even though they did not satisfy entry criteria.
- Developed withdrawal criteria during the study and not withdrawn
- Received wrong treatment or incorrect dose.
- Received excluded concomitant treatment.

When a deviation from the protocol is identified for an individual subject, the investigator or designee must ensure Astellas is notified. Astellas will follow-up with the investigator, as applicable, to assess the deviation and the possible impact to the safety and/or efficacy of the subject and to determine subject continuation in the study.

If a deviation impacts the safety of a subject, the investigator must contact the Sponsor immediately.

The investigator will also assure that deviations meeting IRB/IEC and applicable regulatory authorities' criteria are documented and communicated appropriately. All documentation and communications to the IRB/IEC and applicable regulatory authorities will be provided to the Sponsor and maintained within the Trial Master File (TMF).

NOTE: Other deviations outside of the categories defined above that are required to be reported by the IRB/IEC in accordance with local requirements will be reported, as applicable.

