5.2 Modified Full Analysis Set (mFAS)

The modified full analysis set (mFAS) consists of all subjects who are randomized and received at least one dose of study drug (Astagraf XL or immediate-release tacrolimus), and whose pre-transplant cross-match antibody samples do not demonstrate pre-formed DSA for the duration of the study. This will be the primary analysis set for efficacy assessments, and subjects will be included based on randomized study drug assignment.

The selection of subjects for the mFAS will be confirmed in the Analysis Set Classification Meeting (ASCM) / Data Review Meeting.

The mFAS will be used for summaries and primary analyses of efficacy data, as well as selected demographic and baseline characteristics.

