5.3 Per Protocol Set (PPS)

The Per-Protocol Set (PPS) includes all subjects of the mFAS who do not experience any protocol deviation criteria defined in Section 7.2.2.

Final judgments on exclusion of subjects from the PPS will be made at the ASCM and data review meeting, held prior to database lock.

The PPS will be used for secondary analyses of efficacy data.

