7.2.2 Protocol Deviations

Protocol deviations as defined in the study protocol (Section 8.1.6 Protocol Deviations) will be assessed for all randomized subjects. The number and percentage of subjects with major protocol deviations will be summarized by criterion, (randomized) treatment group, and overall. Protocol deviations will also be summarized by study site. Subjects with more than one major deviation from the same criterion will be summarized once for the corresponding criterion. Any subjects who have more than one major deviation will be counted once in the overall summary. A data listing will be provided for all deviations by site and subject.

All deviations will be assessed as either major or minor according to a final review meeting prior to unblinding.

The protocol deviation criteria will be uniquely identified in the summary table and listing. The unique identifiers will be as follows:

- PD1 - Entered into the study even though they did not satisfy entry criteria,
- PD2 - Developed withdrawal criteria during the study and was not withdrawn,
- PD3 - Received wrong treatment or incorrect dose,
- PD4 - Received excluded concomitant treatment.

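### The auto-crossmatch exception in exclusion criterion 13 depends on items a and b in section 3.3 but on a and d in the synopsis, so some patients with a positive cytotoxic crossmatch are eligible in one place and excluded in the other

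*Protocol*

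**What the plan says.** Criterion 13 is printed twice in the protocol, in the synopsis and in section 3.3, with the same four items:

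- *a*: positive virtual crossmatch
- *b*: positive cytotoxic crossmatch
- *c*: positive flow cytometry crossmatch
- *d*: MFI at or near 1000 on specific anti-HLA antibody testing

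A patient is excluded "as defined by a subject meeting any of the following criteria", so one item is enough. Items *b* and *c* carry a double-asterisk footnote. In both copies it opens by excusing a positive *b* or *c* that comes from a suspected auto-crossmatch. The copies then differ in one letter:

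- Synopsis: "that is not exclusionary as long as *a* and *d* above are not met"
- Section 3.3: "that is not exclusionary as long as *a* and *b* above are not met"

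The summary of changes for Non-Substantial Amendment 2 does not mention this footnote, so neither version is superseded. Section 3.3 ends with the rule "Waivers to the exclusion criteria will NOT be allowed".

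Under Protocol 8.1.6 and SAP 7.2.2, a subject who "Entered into the study even though they did not satisfy entry criteria" is deviation PD1.

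**The concern.** The section 3.3 footnote works against itself. It opens the exception to patients with a positive *b*, then withdraws it if *b* is met. The synopsis version is coherent: a positive cell-based crossmatch can be put down to auto-reactivity when the two tests for antibody specificity, *a* and *d*, are clean.

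Two sites reading different pages could decide differently on the same patient. One following section 3.3 would turn away a patient whom the synopsis accepts. One following the synopsis would enrol a patient who can be flagged PD1 under section 3.3. What follows from PD1 is:

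- **Continuation.** Protocol 8.1.6 has the sponsor follow up "to assess the deviation and the possible impact to the safety and/or efficacy of the subject and to determine subject continuation in the study". Protocol 6.1 collects no further clinical information after discontinuation, apart from adverse event follow-up. SAP 7.4.1.1 drops subjects whose primary endpoint is unknown, undetermined or missing. A continuation decision taken on the wrong wording could therefore cost an endpoint.
- **Per-protocol set.** SAP 5.3 builds the PPS from mFAS subjects without the listed deviations. SAP 7.4.1.2 uses the PPS for a secondary analysis of the primary endpoint, and SAP 7.4 uses it for the risk factor analyses. Removal is not automatic: "Final judgments on exclusion of subjects from the PPS will be made at the ASCM and data review meeting".
- **Primary analysis set.** SAP 5.2 has no deviation criterion for the mFAS: "This will be the primary analysis set for efficacy assessments, and subjects will be included based on randomized study drug assignment". PD1 alone removes no one from the primary analysis.

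**Working it through.** **Inputs.** Items *a* to *d*, the any-one-excludes rule and the two footnotes come from Protocol section 3.3 and the synopsis. The planned 550 subjects, 220 per group, and rates of 20% and 10% come from Protocol 7.1 and SAP 4. The plan gives no figure on the footnote itself to reproduce.

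**Rule.** For a patient whose positive *b* and/or *c* comes from a suspected auto-crossmatch:

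excluded = *a* or *d* or [(*b* or *c*) and the exception does not apply]

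- Synopsis: the exception applies if *a* and *d* are both negative.
- Section 3.3: the exception applies if *a* and *b* are both negative.

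**Enumeration.** There are 2 states of *a*, 2 of *d* and 3 combinations of *b* and *c* with at least one positive: 2 × 2 × 3 = 12 profiles. Three of the four (*a*, *d*) combinations have at least one positive, so 3 × 3 = 9 profiles are excluded in both copies whatever the footnote says. Three remain, all with *a* and *d* negative:

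| *b* | *c* | Synopsis | Section 3.3, neither met | Section 3.3, not both met |
|---|---|---|---|---|
| − | + | eligible | eligible | eligible |
| + | − | eligible | excluded | eligible |
| + | + | eligible | excluded | eligible |

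Read as neither item met, the synopsis accepts 3 of 3 and section 3.3 accepts 1 of 3. The exception helps 2 of 2 of the remaining *b*-positive profiles in the synopsis and 0 of 2 in section 3.3. Read as not both met, none of the 3 differ. With *d* in place of *b* in section 3.3, the copies agree in all 12.

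**Number of patients.** The documents give no frequency of auto-crossmatch positivity. Assuming 0.1% to 2% of planned subjects: 550 × 0.001 = 0.55 and 550 × 0.02 = 11.

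**Power, as an upper illustration.** Take 220 per group, which is the sample-size target and not a stated PPS size. Use the pooled normal approximation with p₁ = 0.20, p₂ = 0.10 and mean 0.15:

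z = [0.10 − 1.96 × √(2 × 0.15 × 0.85 / n)] / √[(0.20 × 0.80 + 0.10 × 0.90) / n]

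- n = 220: z = (0.10 − 1.96 × 0.03405) / 0.03371 = 0.987, power 83.8%
- n = 220 × 0.98 = 215.6: z = (0.10 − 1.96 × 0.03439) / 0.03405 = 0.957, power 83.1%

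Losing 2% of the set costs 0.7 percentage points.

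**The case against.** The strongest reply is that this is a one-letter slip which corrects itself. The section 3.3 condition contradicts its own opening, the protocol prints the sensible version in the synopsis, and a careful reader would see that *d* was meant. The error can only exclude more patients. No one with donor-specific antibody enters because of it, since *a* and *d* each exclude independently. Any PD1 flag can be settled at the review meeting, where SAP 7.2.2 also grades deviations as major or minor. All of this stands, and it limits the weight of the point.

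Three further arguments deserve an answer.

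- **The other reading.** If the phrase means that *a* and *b* are not both met, the copies agree. That reading is strained, because it would make the synopsis condition pointless: *a* or *d* alone already excludes.
- **The waiver bar.** The ban on waivers does not stop a site from asking the sponsor which wording applies. That is a request for clarification, and Protocol 8.1.6 defines a waiver as approval to deviate. The ban does mean that a site bound by section 3.3 cannot simply be granted an exception.
- **A misread letter.** The point rests on one italic letter in a PDF. Nothing shows that it was misread, but it should be confirmed against the signed protocol before the correction is issued.

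The profile counts are logical combinations, not patients, and the 0.1% to 2% range has no anchor in the documents.

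**Conclusion.** The concern holds. Two current statements of the same exclusion rule conflict. On the natural reading, the one in section 3.3 disables the exception for every patient with a positive cytotoxic crossmatch. The conflict covers 2 of the 3 profiles that the footnote can affect: *b* positive, *a* and *d* negative, with *c* either way.

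The practical size is probably small: about 0.6 to 11 of 550 subjects under the assumed 0.1% to 2%. Nothing here affects alpha, and no difference between arms is shown. The point is worth correcting because the rule governs enrolment and the PD1 and PPS decisions. It should be treated as an internal inconsistency in an operative criterion.

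**What to change.** In the double-asterisk footnote to criterion 13 in section 3.3, replace *b* with *d* so that it matches the synopsis. Tell sites by memo. At the review meeting before database lock, judge PD1 for this criterion against the corrected wording. SAP version 2.00 (October 2019) was written after the interim decision, so enrolment may be complete or nearly so. In that case the memo matters less, but the PD1 ruling still needs one agreed text.

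A separate, optional clarification: the single-asterisk footnote discontinues a subject whose physical crossmatch, done within 48 hours of transplant, is positive. It does not say whether the auto-crossmatch exception covers that test. One clause would settle it.

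The cost is one letter, a site memo and, if wanted, one clause. No tests, patients or analyses are added.

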4 TREATMENT(S)

4.1 Identification of Investigational Product(s)

4.1.1 Test Drug(s)

Astellas will provide the following for patients randomized to the Astagraf XL treatment arm for the study duration of up to 24 months:

Astagraf XL 0.5 mg

Oblong capsule with a light yellow cap and orange body. Capsule is branded with red “647” on capsule body and “0.5 mg” on capsule cap. The capsule is supplied in 30-count short, square bottles with brown caps.

Astagraf XL 1 mg

Oblong capsule with a white cap and orange body. Capsule is branded with red “677” on capsule body and “1 mg” on capsule cap. The capsule is supplied in 30-count short, square bottles with blue caps.

Astagraf XL 5 mg

Oblong capsule with a grayish-red cap and orange body. Capsule is branded with red “687” on capsule body and “5 mg” on capsule cap. The capsule is supplied in 30-count short, square bottles with orange caps.

IF medically indicated, subjects randomized to the Astagraf XL treatment arm who are unable to tolerate oral administration of Astagraf XL, may be administered tacrolimus via IV solution (**Prograf** solution for intravenous use), administered as a 24-hour continuous infusion. Administration of IV tacrolimus should be discontinued as soon as the subject can tolerate oral administration, and may not exceed a period of seven consecutive days.

Astagraf XL cannot be given intravenously. Astagraf XL should not be given via NGT due to its extended release characteristics. IV tacrolimus will not be provided by the Sponsor.

